8.4. Number of Subjects

The study will enroll approximately 454 subjects.

8.5. Benefits and Risk Assessment

Patients with advanced melanoma who relapse after immunotherapy (and a BRAF or MEK inhibitor if indicated) have an estimated survival that is measured only in months with no approved therapeutic options. Preliminary experience with the IMO-2125 + ipilimumab regimen is encouraging and the combination appears to be tolerable ([Uemera, 2017](#)). Based on these data, the benefit:risk is likely to be favorable if the efficacy objectives of the study are achieved.

9. STUDY TREATMENTS

9.1. IMO-2125

IMO-2125, a novel phosphorothioate oligodeoxynucleotide, is composed of two strands of modified DNA joined at the 3' ends. IMO-2125 is a hygroscopic white to off-white amorphous solid obtained by lyophilization; it is highly soluble in aqueous media.

IMO-2125 drug product is supplied as an aqueous sterile solution. Each vial contains IMO-2125 sodium salt equivalent to 8 mg/mL of IMO-2125 free acid compounded with 0.9% sodium chloride.

9.2. Ipilimumab

Ipilimumab is a commercially available product.

9.3. Drug Handling and Administration

9.3.1. Drug Delivery to Site

After the research site has submitted all approved regulatory and study start-up documents, an IXRS will be used to manage drug supply. All IMO-2125 shipments are sent refrigerated. Upon receipt, the pharmacist or appropriate technician/designee must inspect the contents, verify temperature conditions, and confirm receipt of goods.

Drug inventory will be maintained by the site. Resupply of IMO-2125 to the sites is detailed in the Pharmacy Manual.

9.3.2. Drug Storage

9.3.2.1. IMO-2125 Storage

Vials of IMO-2125 drug product are to be stored at 2°C to 8°C and storage temperature must be continuously monitored. IMO-2125 must be stored in a securely locked enclosure. Access is strictly limited to the pharmacist or designated study personnel before preparation.

9.3.2.2. Ipilimumab Storage

Refer to locally issued ipilimumab package insert for subjects receiving this agent.

9.3.3. Administration

Subjects will be randomized (1:1) to receive either:

1. Arm A – ipilimumab 3 mg/kg i.v. at Weeks 1, 4, 7, and 10
or
2. Arm B – IMO-2125, 8 mg intratumorally at Weeks 1, 2, 3, 5, 8, 11, 16, 20, and 24 in combination with ipilimumab 3 mg/kg i.v. at Weeks 2, 5, 8, and 11

9.3.3.1. Ipilimumab- Arm A

Ipilimumab will be administered i.v. using a 90-minute infusion duration at 3 mg/kg on Weeks 1, 4, 7, and 10 (Arm A) or Weeks 2, 5, 8, and 11 (Arm B). Cross-over therapy will not be allowed for subjects assigned to Arm A.

9.3.3.2. IMO-2125 + Ipilimumab- Arm B

IMO-2125 will be given prior to ipilimumab on days when both are to be administered. IMO2125 will be administered intratumorally as a 1-4 mL injection to a single designated lesion throughout the study. Subjects will remain at the study site for observation for a minimum of 30 minutes following each administration of IMO2125.

The injected tumor will be selected from (in order of priority) pathologic draining lymph nodes, superficial or s.c. metastases, or deep or visceral metastases, the latter requiring interventional radiology support for both IMO-2125 administration and selection of a lesion that can be safely injected multiple times. The dose will be thoroughly distributed within the injected tumor using a single injection site and a fanning method to ensure even distribution.

Dosing volume will be adjusted on a sliding scale and based on the judgment of the investigator as the injected tumor shrinks to maintain a constant total dose. Additional details are described in the Pharmacy Manual. In the event a full dose can no longer be practically administered into the injected tumor, another tumor may be selected. In the event a complete tumor regression occurs prior to completion of therapy, any remaining IMO-2125 doses should be administered into the tumor bed, except in the case of visceral lesions for which injections should be stopped. Treatment following disease progression is at the discretion of the Investigator. More details on IMO-2125 dose preparation can be found in the Pharmacy Manual.

9.3.4. Dose Modification

The most common AEs following intratumoral administration of IMO-2125 have been non-specific “flu-like” symptoms and mild to moderate injection site reactions. In combination with ipilimumab, IMO-2125 has been associated with irAEs (Section 10.1.3.4) and fever. Ipilimumab dosing will follow the local package insert. IMO-2125 therapy should be continued if ipilimumab is discontinued early for toxicity.

Dose modification instructions for IMO-2125 including its use in combination with ipilimumab are provided in [Table 3](#).

Table 3: Dose Modification Instructions for IMO-2125

Event	Action	Dose Modification
Local or mild systemic reaction (e.g., pyrexia)	Supportive measures as required. Continue treatment with IMO-2125 per clinical discretion.	None
Severe systemic reaction for which more aggressive measures including hospitalization are required (e.g., severe hypotension)	Supportive measures as required. Hold further dosing until the event resolves to baseline or Grade 1 and the re-treatment criteria below are met.	None.
Life-threatening AE (e.g., anaphylaxis)	Supportive measures as required.	Discontinue treatment
Serious procedural complication related to deep or visceral injection (e.g. pneumothorax or hematoma formation)	Supportive measures as required	Discontinue visceral injections (treatment may be continued if a superficial lesion or tumor-involved lymph node is available for injection instead)

Conventional supportive medications (including infliximab for immune-related colitis and growth factor support) are permitted.

Criteria for re-initiation of treatment with each dose of study drug include:

- ANC $\geq 1.5 \times 10^9/L$ (1500/ μL);
- Platelets $\geq 75 \times 10^9/L$ (75,000/ μL);
- Resolution of all clinically significant non-hematologic toxicities for which a causal association to study treatment cannot be ruled out to Grade ≤ 1 or baseline.

If the subject does not meet these criteria, dosing will be delayed, and the subject should be re-evaluated within 48 to 72 hours. If the next dose is delayed by more than 21 days for toxicity, the subject should be removed from study treatment unless approved by the medical monitor.

9.3.4.1. Dose Modifications for Ipilimumab-Related Toxicities

Please refer to the current, locally approved ipilimumab package insert for specific guidance in managing irAEs associated with ipilimumab. [Table 4](#) provides guidance on modifications to ipilimumab dosing for selected toxicities.

Table 4: Recommended ipilimumab dose modifications for selected toxicities

Organ system	Adverse reaction	Treatment modification
Endocrine	Symptomatic endocrinopathy	Withhold ipilimumab Resume ipilimumab in patients with complete or

Organ system	Adverse reaction	Treatment modification
		
partial resolution of adverse reactions (Grade 0 to 1), and who are receiving no more than physiologic doses of systemic steroids per local prescribing information.

Ophthalmologic	
 • Symptomatic reactions lasting 6 weeks or longer • Inability to reduce corticosteroid dose to physiologic doses per local prescribing information 	Permanently discontinue ipilimumab
Enterocolitis	
Grade 2 through 4 reactions
 
 • not improving to Grade 1 within 2 weeks while receiving topical therapy or • requiring systemic treatment 	
Permanently discontinue ipilimumab

Hepatitis Dermatitis Neuropathies Other immune-related toxicities	
Grade ≤ 2
 
Grade 3 or 4
	
Withhold ipilimumab; administer anti-diarrheal treatment and, if persistent for more than 1 week, initiate systemic corticosteroids at a dose of 0.5 mg/kg/day prednisone or equivalent. The use of infliximab is also permitted per institutional policies.
 
Permanently discontinue ipilimumab

	
 • Grade 2 reactions lasting 6 weeks or longer 	Permanently discontinue ipilimumab

Organ system	Adverse reaction	Treatment modification
	
 • Inability to reduce corticosteroid dose to physiologic doses per local prescribing information • Grade 3 or 4 	

If the subject does not meet the criteria for resuming treatment, dosing will be delayed, and the subject should be re-evaluated within 48 to 72 hours. If the next dose is delayed for toxicity by more than the period specified per the locally approved ipilimumab package insert, the subject should be discontinued from study treatment unless approved by the medical monitor.

9.3.4.2. Procedures for Assessment of Subjects with Changes in Complement Levels

Activation of complement in non-human primates is a well-described effect of phosphorothioate oligonucleotides, including IMO-2125. Monkeys are thought to be particularly sensitive to oligonucleotide-induced complement activation and a similar direct oligonucleotide-induced complement activation has not been observed in humans or other species.

Complement samples will be collected at Weeks 1 and 14 for Arm A and Weeks 1 and 11 for Arm B, according to the Schedule of Events table (see [Table 1](#)), and will be analyzed at a central laboratory (Medpace Reference Laboratories). If at any time during study participation, a subject experiences an acute drop in complement (total hemolytic complement assay, complement component 3, or complement component 4) levels $\geq 50\%$ or a drop to an absolute value below the lower limit of normal with reference to baseline testing or most recent values on study, the Sponsor will notify the site and the following procedures should be performed by the investigator:

1. Perform a safety evaluation and any necessary testing for the subject as clinically indicated.
2. If the results of the safety evaluations suggest any safety concerns associated with the drop in complement levels, hold the study drug treatment.
3. The patients should return to the clinic to have another serum sample drawn and sent to the central laboratory to confirm decreased complement levels.

Based on the results of this work-up and the subject’s disease assessment/response to study drug, the Investigator, in discussion with the Sponsor’s Medical Monitor, will determine the subject’s risk/benefit profile and discuss appropriate next steps regarding the subject’s continued treatment with study drug.

9.3.4.3. Procedures for Assessment of Subjects with Symptomatic Thrombocytopenia

Severe thrombocytopenia has been reported in clinical studies with another oligonucleotide ([FDA Briefing Document, 2015](#)). Most of these subjects had confirmed anti-platelet antibodies. These cases occurred 14 to 26 months after the onset of treatment, suggesting that risk increases with duration of exposure. In the event of a precipitous drop in platelet counts (i.e., to $<25 \times 10^9/L$), treatment with IMO-2125 should be held and an anti-platelet antibody count

obtained. Treatment may be resumed once administration criteria (Section 9.3.4) are met. Anti-platelet, thrombolytic, or anticoagulant drugs should be used with caution.

9.4. Labeling

The product label contains the elements required by national and local authorities for investigational products. IMO-2125 will be shipped directly to the Investigator site.

9.5. Drug Accountability

The Investigator is responsible for study drug accountability, reconciliation, and record maintenance. In accordance with all applicable regulatory requirements, the Investigator or designated study personnel (e.g., Pharmacy) must maintain study drug accountability records throughout the study. Further details are provided in the Pharmacy Manual.

9.6. Concomitant and Prohibited Medications

9.6.1. Concomitant Medications

With the exception of the prohibited drugs listed in Section 9.6.2, concomitant prescription medications and over-the-counter drugs are permitted, including infliximab and growth factor support. These should be recorded on the eCRF.

9.6.2. Prohibited Medications

The following medications are prohibited while the subject is in this study:

- Anti-cancer therapies other than those specified in the protocol (see Section 7.2 for inclusion criteria related to anti-cancer therapies)
- Oncolytic tumor viral therapies (e.g., Imlygic[®])
- Investigational/experimental medicines or vaccines

10. ADVERSE EVENT REPORTING

10.1. Adverse Events

Adverse events should be assessed continuously throughout the study and recorded on the eCRF. During the Follow-up Periods, for 90 days after the last dose of study treatment, all SAEs, irAEs (Section 10.1.3.4), AEs Grade ≥ 3 , and associated concomitant medications for their treatment must be reported. For the remainder of the Follow-up Periods, AE reporting may be limited to treatment-related Grade ≥ 3 AEs and SAEs, and the associated concomitant medications (see Table 1 and Table 2).

10.1.1. Definition of Adverse Events

10.1.1.1. Adverse Event

An AE is any untoward medical occurrence temporally associated with the use of a medical product in a subject, *whether or not* the event is considered causally related to the medical product.¹ An AE can be a new occurrence or an existing process that increases significantly in intensity or frequency.

10.1.1.2. Serious Adverse Event

An AE is **serious** when the subject outcome is one or more of the following:

- Death.
- Life-threatening, meaning that the subject was at immediate risk of death from the event at the time that the event occurred. It does not include an event which hypothetically might have caused death if it occurred in a more severe form.
- Hospitalization, initial or prolonged, meaning that a hospital admission and/or prolongation of a hospital stay was required for the treatment of the AE, or occurred as a consequence of the event. It does not include a pre-planned elective hospital admission for treatment or diagnostic procedures, or, in general, a hospital admission of less than 24 hours duration.
- Disability or incapacity that is persistent or significant.
- Congenital anomaly or birth defect.
- Important medical event that, although not immediately life-threatening, requires intervention in order to prevent one of the other serious outcomes listed above. Examples of such events are allergic bronchospasm requiring intensive treatment in an emergency room or at home; blood dyscrasias or convulsions that do not result in hospitalization; or the development of drug dependency or drug abuse.

¹ A medical product may be a drug or a device being used either prior to or after regulatory approval. The medical product in this protocol will hereafter be referred to as study drug (synonym: investigational agent).

10.1.1.3. Suspected Unexpected Serious Adverse Reaction (SUSAR)

A SUSAR is defined as an SAE that meets *both* the following criteria with respect to study drug:

- *Suspected* — is assessed as related or possibly related to study drug (see [Section 10.1.3.3](#));
- *Unexpected* — compared to the study drug-related AEs described in the Investigator’s Brochure, the event meets *any* of the following criteria:
 - The event was not previously described;
 - The event is now characterized as more severe (see [Section 10.1.3.5](#));
 - The event is now characterized more specifically (e.g., an event of “interstitial nephritis” in a subject receiving an agent previously described as associated with “acute renal failure”).

In clinical trials involving ill subjects, events considered related to the natural history of the disease under study or to lack of efficacy (that is, the event is considered more likely related to those factors than to other factors, including study drug) are not considered "unexpected."

10.1.2. Recording Adverse Events

Procedures for the collection and recording of AEs are as follows:

- AEs are captured from the time of informed consent. Events will be recorded in the AE portion of the electronic data capture (EDC), with particular attention to whether the onset of the event was before or after the administration of the first dose of study drug. All recorded events will be included in applicable line listings, but only events with onset after administration of the first dose will be included in summaries of TEAEs.
- After the Active Follow-up Period, surveillance will be passive (only events brought to the Investigator’s attention will be considered) and only events assessed as SUSARs will be recorded (see [Section 10.1.1.3](#)).
- In accordance with the FDA guidance document – Safety Reporting Requirements for Investigational New Drugs and Bioavailability/Bioequivalence Studies – disease progression does not require reporting as an AE or SAE. However, signs and symptoms related to disease may be reported at the discretion of the Investigator.

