5. Subjects must be randomized within 28 days after signing the ICF; the first dose of study drug should be administered within 2 days after randomization.
6. CBC and chemistries do not have to be repeated if Screening tests are completed within 7 days of start of treatment.
7. Samples will be collected pre-dose, and at 1, 2 and 4 hours (± 10 minutes) post-dose.
8. PT, aPTT, INR.
9. Vital signs will include systolic and diastolic blood pressure, body temperature, pulse rate, body weight, and height (Week 1 only). Vital signs should be completed prior to treatment administration.
10. WOCBP only. Pregnancy test after randomization should be completed as deemed necessary by the Investigator or required by local law.
11. IMO-2125 should be administered prior to ipilimumab.
12. During the IMO Maintenance Period, all CTCAE Grade ≥ 2 irAEs and laboratory abnormalities (regardless of relationship to study drug) should be monitored until resolution, stabilization, or return to baseline. During the Follow-up Periods, for 90 days after the last dose of study treatment, all SAEs, irAEs, AEs Grade ≥ 3 , and associated concomitant medications for their treatment must be reported. For the remainder of the Follow-up Periods, AE reporting should be limited to Treatment-related Grade ≥ 3 AEs and SAEs, and the associated concomitant medications.
13. Blood samples for evaluation of plasma IMO-2125 concentrations will be collected pre-dose and at 1, 2, and 4 h post-dose (± 30 minutes) at Week 1 and Week 11 only.
14. Serum samples will be collected for analysis of anti-IMO-2125 and anti-ipilimumab antibodies; details are provided in the Laboratory Manual. Baseline sample to be collected at Week 1 before the first dose of study treatment.
15. Optional (see Laboratory Manual).
16. To inform treatment management decisions, disease assessments are to be completed at Week 12 (± 1 week), then every 8 weeks (± 2 weeks) for the first year and every 12 weeks (± 2 weeks) during subsequent years.
17. To minimize bias in the PRO data, disease and PRO assessments are to be completed prior to study drug administration and AE evaluations at Weeks 1, 8, and 12 (± 1 week), then every 8 weeks (± 2 weeks) for the first year and every 12 weeks (± 2 weeks) during subsequent years.
18. Per institutional practices following the frequency of active follow-up disease assessments.

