8.3. Study Drug Discontinuation and Study Withdrawal

8.3.1. Subject Discontinuation of Study Drug

Failure to complete Week 10 of study drug (Arm A) or Week 24 (Arm B) for any reason will be considered premature study drug discontinuation. Reasons for premature study drug discontinuation include PD (by irRECIST or by clinical progression), death, intolerable AE, withdrawal of consent, lost to follow up, Investigator discretion, Sponsor decision, and premature termination of the study.

Subjects who discontinue treatment prematurely prior to progression should continue to be followed according to the SOE (Active Follow-up). The Investigator will document the date of and reason(s) for study treatment discontinuation on the electronic case report form (eCRF). Once a subject discontinues study treatment permanently, they will not be able to be retreated.

Subjects who complete the planned study treatment and who have not progressed or started new anti-cancer therapy will enter the Active Follow-up Period and be followed according to the SOE. Subjects will enter the Survival Follow-up Period at disease progression or the start of new anti-cancer therapy (with or without disease progression).

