## 9.5 CONCOMITANT MEDICATIONS

Concomitant medications will be coded using the World Health Organization (WHO) Drug Dictionary Version B3 Sep 2020. A concomitant medication is defined as any drug or substance administered between the time of the first dose of study treatment and 30 days from the date of the last dose of study treatment, or taken to treat SAEs, irAEs, AEs of Grade 3 or above that occurred within 90 days of the last dose of study treatment, or taken to treat Grade 3 or above treatment-related AEs and SAEs that occurred during either the Active or Survival follow-up periods. This includes medications that were started prior to screening if their use continued during dosing. If the start date or end date of concomitant medication is partial, use the imputation rules defined in [Section 8.1.2](#) to impute the date and determine if the medication was concomitant.

In the summary of concomitant medications, each subject is counted once within each unique term. For example, if a subject takes Amoxicillin on two separate occasions, the subject is counted only once under the ingredient “Amoxicillin”.

The summary of concomitant medications using the Safety Set will show the number and percentage of subjects taking concomitant medications by therapeutic class and preferred term (PT). Anatomical Therapeutic Chemical (ATC) Level 4 will be used for the listing and summary.

Idera Pharmaceuticals, Inc.  
 Statistical Analysis Plan  
 Protocol Number: 2125-MEL-301

A similar summary will also be generated for concomitant medications that were used to treat immune-related adverse event as recorded on the Concomitant Medication eCRF page.

Another summary will be generated by category of concomitant immune-modulating medications that were used to treat irAEs. These medication categories include thyroid hormone replacement therapies, systemic steroids, and immune-suppressants. Thyroid hormone replacement therapies will be identified by WHO drug ATC prefix H03, systemic steroids by WHO drug ATC prefix H02, and immuno-suppressants by WHO drug ATC prefix L04. Any medications with one of these prefixes that were indicated on the Concomitant Medication eCRF page as being used to treat irAEs will be included in this summary by preferred term under the corresponding category.

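### Protocol 10.1.2 limits recording after Active Follow-up to SUSARs, contradicting the 90-day and later AE rules in Protocol 10.1, the schedule footnotes and SAP 9.5

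*Protocol*

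**What the plan says.** Two rules for recording adverse events after treatment stand in the current Protocol.

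- **Protocol 10.1.2 (Recording Adverse Events), second bullet.** "After the Active Follow-up Period, surveillance will be passive", meaning that only events brought to the investigator's attention are considered, and "only events assessed as SUSARs will be recorded". The bullet has no 90-day exception and does not refer back to 10.1.
- **Protocol 10.1 (Adverse Events).** "During the Follow-up Periods, for 90 days after the last dose of study treatment, all SAEs, irAEs" and AEs of Grade 3 or higher must be reported, with the medications used to treat them. Then: "For the remainder of the Follow-up Periods, AE reporting may be limited to treatment-related Grade" 3 or higher AEs and SAEs.
- **Table 1 footnote 10 and Table 2 footnote 12.** The same 90-day rule, followed by "For the remainder of the Follow-up Periods, AE reporting should be limited to Treatment-related Grade" 3 or higher AEs and SAEs. The SAP repeats both footnotes in its schedules (SAP 16.1).

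Three other passages bear on how these interact.

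- **Protocol 8.3.1:** "Subjects will enter the Survival Follow-up Period at disease progression or the start of new anti-cancer therapy (with or without disease progression").
- **Protocol 10.1.1.3:** a SUSAR must be serious, assessed as related or possibly related, and unexpected relative to the Investigator's Brochure.
- **SAP 9.5:** concomitant medications include those given for SAEs, irAEs and Grade 3 or higher AEs within 90 days of the last dose. They also include those given for Grade 3 or higher treatment-related AEs and SAEs "that occurred during either the Active or Survival follow-up periods".

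**The concern.** Both rules apply to a subject in Survival Follow-up, and they ask for different things. Because progression or new therapy triggers the move, it can fall well inside the 90 days after the last dose. A site working from 10.1.2 would then stop recording everything except SUSARs. A site working from 10.1 or the schedule footnotes would keep the full list.

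Two things are at stake. First, events that 10.1 requires could be missing from the AE database. Second, sites could collect different data under the same protocol, and any difference between arms in when subjects progress would then become a difference in how completely their events are recorded. Immune-related events are a named safety concern for this combination (Protocol 9.3.4 and 10.1.3.4), so completeness in this window matters when the arms are compared.

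**Working it through.** The plan states no figure to reproduce. The check sets the texts side by side and then does day arithmetic.

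**1. Do the two rules overlap?** They would not if 10.1 covered only Active Follow-up and 10.1.2 only Survival Follow-up. That reading fails. Section 10.1 and the footnotes speak of Follow-up Periods in the plural, the schedules show exactly two (Active and Survival), and SAP 9.5 names both. The overlap is therefore Survival Follow-up. It continues after day 90, because 10.1 still asks for treatment-related Grade 3 or higher AEs and SAEs for the remainder.

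**2. What would SUSAR-only recording leave out?** Applying the three SUSAR conditions to the list in 10.1:

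- a non-serious irAE fails on seriousness;
- a non-serious Grade 3 or higher AE fails on seriousness;
- an unrelated SAE fails on suspicion;
- a serious related event that counts as expected fails on unexpectedness.

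**3. How much of the 90 days is exposed?** Inputs: last Arm A ipilimumab dose at Week 10; Arm B ipilimumab doses ending at Week 11 and IMO-2125 doses running to Week 24 (Protocol 9.3.3); tumor assessment at Week 12 (±1 week), then every 8 weeks in the first year (Protocol 11.1); irPD confirmed at least 4 weeks later (Protocol 11.1 and 20.3).

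Day of Week w = 7(w − 1) + 1. Days exposed = 90 − (day of move − day of last dose).

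| Arm, last dose | Move to Survival Follow-up | Elapsed | Exposed |
|---|---|---|---|
| A, Week 10 (day 64) | Week 11 (day 71), early edge of window | 7 | 83 (92%) |
| A, Week 10 | Week 12 (day 78) | 14 | 76 (84%) |
| A, Week 10 | Week 13 (day 85), late edge of window | 21 | 69 (77%) |
| A, Week 10 | Week 16 (day 106), after confirmation | 42 | 48 (53%) |
| A, Week 10 | Week 20 (day 134) | 70 | 20 (22%) |
| B, Week 11 (day 71) | Week 12 (day 78) | 7 | 83 (92%) |
| B, Week 11 | Week 13 (day 85) | 14 | 76 (84%) |
| B, Week 11 | Week 16 (day 106), after confirmation | 35 | 55 (61%) |
| B, Week 24 (day 162) | Week 28 (day 190) | 28 | 62 (69%) |

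The progression weeks are scenarios built on the planned schedule, not forecasts. The Arm B Week 16 row assumes that no Week 16 dose is given.

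**4. Does 10.1.2 reach every subject?** Not clearly. Under footnote 3 to each schedule, subjects enter Active Follow-up after completing treatment, or after stopping for a reason other than progression or new therapy. A subject who stops for progression goes straight to Survival Follow-up. An Arm B subject progressing at Week 12, with maintenance doses still due, is such a case. The 10.1.2 bullet begins at the end of a period which that subject never entered, so the text does not settle which rule applies.

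**The case against.** The strongest reply is that 10.1.2 is one outlying sentence. The 90-day rule appears three times in the Protocol as something that must be reported, and again in the SAP schedules, so most sites may follow it. SAEs also have their own route: Protocol 10.1.4.2 and 10.1.4.4 require a form within 24 hours and set no end date. Both points stand. They make the loss conditional, and they mean that SAEs may still be captured. They do not cover non-serious irAEs or non-serious Grade 3 or higher AEs, and they do not say which text prevails.

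A second reply is that management follows irRECIST and that treatment may continue past progression at the investigator's discretion (Protocol 9.3.3.2 and 11.1). This can delay the move or shift the last-dose date. It also stands, and it is why a range is given: 76 and 83 days at Week 12 are toward the early end.

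Three stronger readings are tempting, and the documents do not support them.

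- *Early progression will be common because the planned ORR is 12% and 24%.* Non-response includes stable disease and non-evaluable subjects, and no PFS or progression-rate assumption is given.
- *Known ipilimumab irAEs are the ones lost.* Expectedness is judged against the Investigator's Brochure, which is not among the documents.
- *The SAP's safety analyses rest on the 90-day rule.* Only the concomitant-medication definition in SAP 9.5 does. The treatment-emergent definitions in SAP 8.2.7 and 11 have no end date.

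**Conclusion.** Protocol 10.1.2 is wrong as written. It is an internal inconsistency that should be corrected, not a defensible design choice. It conflicts with Protocol 10.1, both schedule footnotes and SAP 9.5, both inside the 90 days and afterwards, and no text resolves the conflict.

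If a site follows 10.1.2, and if the bullet is taken to cover the subject concerned, SUSAR-only recording would apply to 20 to 83 of the 90 days in the Arm A scenarios and 55 to 83 in the Arm B scenarios. More than half the window is exposed when the move comes by Week 16, but only 22% when an Arm A subject moves at Week 20. The number of subjects and events affected cannot be estimated from the documents. The defensible statement is that safety data could be incomplete and inconsistent across sites, not that they will be.

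**What to change.** Reconcile the second bullet of Protocol 10.1.2 with Protocol 10.1, Table 1 footnote 10, Table 2 footnote 12 and SAP 9.5, so that a single AE recording rule covers both Follow-up Periods. The rule should say explicitly what applies to subjects who stop for progression or new therapy and go straight to Survival Follow-up. Tell sites which text governs.

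The cost is a one-sentence protocol clarification and a site notice. No sample size, endpoint or efficacy analysis changes.
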